#### **7.7.9. Safety Analysis**

Safety variables will be tabulated and presented for all patients in the Safety population. AEs will be categorized by system organ class and Preferred Term from the current version of MedDRA. AEs will be summarized overall, by seriousness, severity, and relationship to treatment. Incidence of AEs will be presented overall, by system organ class and preferred term. Severity and relationship to study drug of the incidence of AEs will also be presented. AEs causing study drug withdrawal and/or early study discontinuation and incidence of SAEs will be summarized.

Changes from baseline in vital signs and laboratory parameters, and shifts from baseline in laboratory parameters will be summarized by treatment. Descriptive statistics and frequency tables will be prepared as appropriate for laboratory measurements.

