## 4.0 Introduction

This statistical analysis plan (SAP) describes the statistical methods to be used during the reporting and analyses of data collected under Cutaneous Life Sciences, Inc. Protocol CLS006-CO-PR-002.

This SAP should be read in conjunction with the study protocol and case report form (CRF). This version of the plan has been developed using the protocol dated 23May2017 and CRF dated 02Aug2017. Any further changes to the protocol or CRF may necessitate updates to the SAP.

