## Treatment-related Adverse Events

Any AE with a relationship to study treatment of “Possibly Related” or “Definitely Related” or missing will be considered a treatment-related AE as determined by the Investigator.

## Study Day 1

The first day of medication administered.

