#### **12.6.1 Adverse Events**

Any condition, event and/or signs and symptoms occurring after signing the informed consent form and before starting study drug treatment should be recorded as medical history in the eCRF. Medical conditions/diseases are considered AEs only if they worsen after starting study drug treatment (first application of study drug).

Therefore, An AE includes any condition (including a pre-existing condition) that: 1) was not

---

present prior to study treatment, but appeared or reappeared following initiation of study treatment, or 2) was present prior to study treatment, but worsened during study treatment.

A treatment-emergent adverse event (TEAE) is defined as an AE with onset date at or after the first dose administration of treatment, but no more than 30 days after the last dose of study medication. Only TEAEs will be included in the summary tables.

Adverse events will be coded using MedDRA version 21.0, as applicable at time of analysis. All reported AEs will be coded to the appropriate SOC and PT according to MedDRA Version 21.0.

The relationship of an AE to study drug is to be assessed according to the following definitions:

- Not Related – no temporal association or the cause of the event has been identified, or the drug cannot be implicated based upon available information.
- Possibly Related – temporal association, but other etiologies are likely to be the cause. However, involvement of the drug cannot be excluded, based upon available information.
- Definitely Related – established temporal or other association (e.g., re-challenge) and event is not reasonably explained by the subject's known clinical state or any other factor, based on available information.

The severity of an AE is to be scored according to the following scale:

- Mild - Awareness of sign or symptom, but easily tolerated
- Moderate - Moderate Discomfort enough to cause interference with usual activity
- Severe - Severe Incapacitation with inability to work or perform usual activity

A high level overall summary of TEAEs will be presented to summarize AEs in any category.

Subject incidence of the following AEs will be tabulated by SOC (descending order of frequency) and PT (descending order of frequency). The number and percentage of each TEAE will be calculated.

- TEAEs
- severe TEAEs
- treatment-related TEAEs
- maximum severity of TEAEs
- TEAE with an outcome of death
- TEAE leading to discontinuation of study treatment

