- TEAE leading to discontinuation of the study

Subject incidence of the following AEs will be tabulated by PT in descending order of frequency:

- TEAEs

---

- TEAEs experienced by  $\geq 2$  subjects (for any treatment)
- treatment-related TEAEs by  $\geq 2$  subjects (for any treatment)

Subjects will be counted only once within each SOC or PT. For tables categorized by severity, subjects with multiple events within a particular SOC or PT will be counted under the category of their most severe event for that SOC or PT. Treatment-related TEAEs included AEs from AE CRF page where relationship to study treatment is checked with either 'Possibly Related' or 'Probably Related'. Missing values for severity will be assigned as 'Severe' and missing value for relationship to treatment will be considered as 'Related' in the summary.

AEs leading to discontinuation of treatment are those with an action taken with study treatment on the AE CRF page of "Drug Withdrawn".

AEs leading to discontinuation from the study are those on the AE CRF page of "YES" to the question "Did the adverse event cause the subject to be discontinued from the study?".

By-subject listings will be provided for the following: All AEs, All TEAE, TEAEs leading to discontinuation of treatment and TEAEs leading to discontinuation of the study.

The duration of AEs will be derived as the AE end date (including imputation date for incomplete AE end date) – AE onset date (imputed date for incomplete AE onset date) +1.

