#### AEs of Special Interest (AEOSI)

Study personnel should question and observe subjects for evidence of AEs paying particular attention to local application site reactions and any potential cardiovascular or hematologic AEs.

Subject incidence of the following AEs will be tabulated by SOC (descending order of frequency) and PT (descending order of frequency). The number and percentage of each TEAE will be calculated.

- TEAE of special interest
- Serious TEAE of special interest
- TEAE of special interest leading to discontinuation of study treatment
- TEAE of special interest related to study drug
- Preferred terms used to identify adverse events of special interest (AEOSIs) will be provided by the medical team after a review of AEs appearing in the following system organ classes: general disorders and administration site conditions, cardiac disorders, blood and lymphatic system disorders, renal and urinary disorders, investigations, skin and subcutaneous tissue disorders, and metabolism and nutrition disorders. All AEOSIs will also be provided in a by-subject listing. Preferred terms used to identify adverse events of special interest (AESIs) will be determined by the medical team before database freeze. All AEOSIs will be provided by-subject listing.

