#### **12.6.2 Deaths and Serious Adverse Events**

Serious TEAEs will be summarized by SOC and PT for the All-Treated analysis set.

A further summary of treatment-related SAEs will be provided for the All-Treated analysis set.

---

A table presenting the number and subjects who died during the study will be presented for the All-Treated analysis set.

By-subject listings will be provided for the following: All Deaths, SAEs.

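### SAP 12.6.1 builds the treatment-related TEAE tables from a causality category that is not on the trial's scale and leaves out 'Definitely Related'

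*SAP*

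**What the plan says.** Protocol 7.5.6.2 sets a three-level causality scale: Not Related, Possibly Related, Definitely Related. SAP 12.6.1 repeats it and describes the top level as "established temporal or other association (e.g., re-challenge) and event is not reasonably explained" by the subject's known state or other factors. Neither document has a 'Probably Related' level.

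The SAP then gives two rules for which events count as treatment-related:

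- SAP 8.0, under its own heading, counts events rated Possibly Related, Definitely Related "or missing will be considered a treatment-related AE as determined by the Investigator".
- SAP 12.6.1, just after its list of AE tables, takes them from the AE CRF page where the relationship is "checked with either 'Possibly Related' or 'Probably Related". Its next sentence adds that a "missing value for relationship to treatment will be considered as 'Related' in the summary".

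Related events also appear in two later outputs. One is a table of "TEAE of special interest related to study drug". The other is in SAP 12.6.2: "A further summary of treatment-related SAEs will be provided for the All-Treated analysis set". Protocol 7.7.9 makes the underlying commitment: "Severity and relationship to study drug of the incidence of AEs will also be presented".

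SAP 4.1 declares no changes from the protocol, and SAP 4.0 says the SAP is to be read together with the protocol and the CRF.

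**The concern.** The sentence in 12.6.1 is an operative derivation rule. It names the data source and sits beside the tables that use it, so a programmer could reasonably code from it. Coded as written against the documented scale, the term 'Probably Related' would match nothing and 'Definitely Related' would not be selected. The related tables would then include events for which no causality was recorded and exclude those that the investigator attributed most firmly to study drug. That defeats the conservative intent of counting missing as related. Two programmers working from different sections could also produce different tables, each able to point to the SAP.

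What is at stake is the investigator-attributed part of the safety report. The SAP lists no table by causality level, so among the tables whose content is specified, the related ones are what meet the commitment in Protocol 7.7.9.

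**Working it through.** The plan states no figure on this point. The check sets the rules side by side against the documented scale.

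| Recorded relationship | On the scale (Protocol 7.5.6.2; SAP 12.6.1)? | Related under SAP 8.0? | Related under the SAP 12.6.1 sentence? |
|---|---|---|---|
| Not Related | Yes | No | No |
| Possibly Related | Yes | Yes | Yes |
| Probably Related | No | Not named | Yes, but matches no level |
| Definitely Related | Yes | Yes | **No** |
| Missing | n/a | Yes | Yes |

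SAP 8.0 selects {Possibly, Definitely, missing}. SAP 12.6.1 taken literally selects {Possibly, missing}. The difference is exactly {Definitely}. The two sections agree on missing values. Nothing in either document equates 'Probably' with 'Definitely' or ranks the two rules.

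**Tables affected.** Counting those listed in SAP 12.6.1 and 12.6.2, apart from the high-level overall summary:

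- By SOC and PT: 7
- By PT only: 3
- AEs of special interest: 4
- Deaths and SAEs: 3 (serious TEAEs, treatment-related SAEs, deaths)
- Total: 7 + 3 + 4 + 3 = 17

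Two are governed directly by the sentence: treatment-related TEAEs by SOC and PT, and treatment-related TEAEs in at least 2 subjects by PT. Two are conditional: related AEs of special interest and treatment-related SAEs. These change only if they share the flag, and SAP 12.6.2 does not cite the sentence. The remaining 17 − 2 − 2 = 13 do not use causality.

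**Illustrative size only.** Protocol 5.2 reports 53 mild + 2 moderate = 55 AEs in Phase 2, with 47 rated unlikely related or unrelated.

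- Remainder: 55 − 47 = 8, or 8/55 = 14.5%
- Per subject: 8/80 = 0.10
- At 480 subjects: 0.10 × 480 = 48 related events
- If 10%, 25% or 50% of these were rated Definitely Related: 4.8, 12 or 24 events left out

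The shares of 10% to 50% are assumptions, since the documents give none. The calculation also assumes that the 55 AEs and the 47 TEAEs count the same set of events, and that a rate pooled over four Phase 2 arms, with a different causality scale and shorter follow-up, carries over. It counts events, whereas the tables count subjects once per SOC or PT. The finding does not depend on it.

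**The case against.** The strongest reply is that the SAP already contains the right rule. Section 8.0 is the formal definition, and the three-level scale stands in the same section as the faulty sentence. To lose events, a programmer would have to ignore both and code a category that neither contains. SAP 11.2 provides for pre-freeze and post-freeze table runs, the latter discussed with the sponsor, and SAP 13.0 refers to a quality control plan. A wrong final table is therefore unlikely. Most of the safety output does not depend on causality, and efficacy, alpha and sample size are untouched.

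Much of this stands. It limits the consequence, and it is why the claim is that events could be omitted rather than that they will be. It does not remove the conflict: those checks work from the SAP, and the SAP gives two answers.

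A second reply is that the CRF, which is not among the documents reviewed, may offer 'Probably Related'. In that case swapping the word would itself mis-specify the derivation, and so would a bare cross-reference to 8.0. This also stands, as a point about the order of the remedy: the CRF check should come first. A CRF with that option would depart from the protocol scale and would need reconciling in any event.

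A third reply is that the Phase 2 projection is not informative, being in events, on another scale and with assumed shares. That is accepted; it carries no weight in the conclusion.

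**Conclusion.** The concern holds. The treatment-related derivation in SAP 12.6.1 contradicts SAP 8.0, the scale in 12.6.1 itself and Protocol 7.5.6.2. Applied literally to the documented scale, it omits exactly the 'Definitely Related' events. Two of the 17 listed tables are exposed directly and two more conditionally. Tables of all, severe, serious and discontinuation TEAEs, the overall special-interest table and the listings do not select on this flag, so between-arm event rates stay visible.

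The textual conflict is certain. The consequence depends on which rule is programmed and on the CRF response options, which could not be checked. The number of events is unknown. The point should be fixed because it concerns safety attribution and costs almost nothing to correct; it does not threaten the trial's main conclusions.

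**What to change.** 1. Check the relationship options on the AE CRF page against the three-level scale. If they differ, reconcile the CRF with the protocol and document how each recorded value maps to the scale.
2. If they match, change 'Probably Related' to 'Definitely Related' in SAP 12.6.1, or replace the sentence with a cross-reference to the definition in SAP 8.0. The rule for missing values needs no change.
3. State that this single derivation feeds the treatment-related TEAE tables, the related special-interest table and the treatment-related SAE table.

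Do this before the derivation is programmed, and in any case before unblinding. If the CRF matches the scale, the cost is one word or one cross-reference, one clarifying sentence and the matching line in the derivation specification. No new data or analysis is needed.

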#### AEs of Special Interest (AEOSI)

Study personnel should question and observe subjects for evidence of AEs paying particular attention to local application site reactions and any potential cardiovascular or hematologic AEs.

Subject incidence of the following AEs will be tabulated by SOC (descending order of frequency) and PT (descending order of frequency). The number and percentage of each TEAE will be calculated.

- TEAE of special interest
- Serious TEAE of special interest
- TEAE of special interest leading to discontinuation of study treatment
- TEAE of special interest related to study drug
- Preferred terms used to identify adverse events of special interest (AEOSIs) will be provided by the medical team after a review of AEs appearing in the following system organ classes: general disorders and administration site conditions, cardiac disorders, blood and lymphatic system disorders, renal and urinary disorders, investigations, skin and subcutaneous tissue disorders, and metabolism and nutrition disorders. All AEOSIs will also be provided in a by-subject listing. Preferred terms used to identify adverse events of special interest (AESIs) will be determined by the medical team before database freeze. All AEOSIs will be provided by-subject listing.

#### **12.6.2 Deaths and Serious Adverse Events**

Serious TEAEs will be summarized by SOC and PT for the All-Treated analysis set.

A further summary of treatment-related SAEs will be provided for the All-Treated analysis set.

---

A table presenting the number and subjects who died during the study will be presented for the All-Treated analysis set.

By-subject listings will be provided for the following: All Deaths, SAEs.

### **12.6.3 Laboratory Data**

Laboratory test results are reported in International System of Units (SI).

Descriptive summaries of changes from baseline for each laboratory test listed below will be provided for numerical laboratory assessments by visit.

Laboratory shift tables from baseline to each post baseline visit for lab values evaluation of 'High' 'Low' or 'Normal', when available, will be planned when the baseline results are available. The categorical lab results will be summarized by frequency and percentage and by visit.

The clinical safety laboratory tests will include the following parameters:

- Hematology: hemoglobin, hematocrit, red blood cell (RBC) including mean corpuscular volume (MCV) and red cell distribution width (RDW), white blood cell (WBC) count with differential (neutrophils, lymphocytes, monocytes, eosinophils, basophils), and platelet count.
- Chemistry/Lipids:
  - General: calcium, glucose, lactate dehydrogenase (LDH)
  - Electrolytes: carbon dioxide (bicarbonate), chloride, magnesium, sodium, potassium
  - Kidney/Liver: blood urea nitrogen (BUN), creatinine, uric acid, total protein, aspartate aminotransferase (AST), alanine aminotransferase (ALT), albumin, alkaline phosphatase (ALP), gamma glutamyl transferase (GGT), total bilirubin
  - Lipids: total cholesterol, high-density lipoproteins (HDL), low-density lipoproteins (LDL), triglycerides

### **12.6.4 Vital Signs**

Vital signs (blood pressure [BP], heart rate [HR]) will be measured at each visit during Screening, Double-blind Treatment and Post-treatment Efficacy Evaluation Periods.

Observed values and changes from baseline in vital signs will be summarized by vital sign parameter and visit. Descriptive statistics will be shown for baseline, each post-baseline time point, and the change from baseline to each post-baseline time point.

### **12.6.5 Physical Examinations, ECGs, and Other Observations Related to Safety**

A limited physical exam and only baseline ECG are conducted in this study.

Physical exam, ECG, and urine pregnancy test data will be listed.

## 13.0 Validation

PRA's goal is to ensure that each TFL delivery is submitted to the highest level of quality. Our quality control procedures will be documented separately in the study specific quality control plan.

## Appendix 1 Glossary of Abbreviations

Glossary of Abbreviations:	
AE	Adverse Event
AEOSI	Adverse Event of Special Interest
ALT	Alanine aminotransferase
ANCOVA	Analysis Of Covariance
AST	Aspartate aminotransferase
BOCF	Baseline Observation Carried Forward
BP	Blood pressure
BUN	Blood urea nitrogen
CBC	Complete blood count
CLS	Cutanea Life Sciences, Inc.
CLS006	Furosemide Topical Gel 0.125% w/w
CMH	Cochran-Mantel-Haenszel
ECG	Electrocardiogram
eCRF	Electronic Case Report Form
EOS	End of Study
EOT	End of Treatment
ET	Early Termination
GGT	Gamma glutamyl transferase
HDL	High-density lipoproteins
HR	Heart rate
ITT	Intent-to-Treat
IWRS	Interactive Web Response System
LDH	Lactic dehydrogenase
LDL	Low-density lipoproteins
MedDRA	Medical Dictionary for Regulatory Activities
MI	Multiple Imputation
PI	Principal investigator
PP	Per Protocol
RBC	Red blood cell
SAE	Serious Adverse Event
SD	Standard Deviation
TEAE	Treatment emergent adverse events
WBC	White blood cell
w/w	Weight for weight
